9.1 Data Handling After Cut-off Date

By its nature, data after cut-off may be incomplete and subject to further change and will not be used for summary statistics, statistical analyses, listings or imputations.

Stop dates and outcomes of adverse events are not affected by this rule, e.g., a stop date of AEs, and its related outcome which starts prior to the cut-off, but stops after date of cut-off, will not be changed.

9.2 Definition of Baseline and Change from Baseline

The last non-missing measurement prior to the first study treatment administration will be used as the baseline measurement for safety and efficacy analyses.

If an assessment that is planned to be performed before treatment per protocol is performed on the same day as the start of treatment, respectively, but the assessment time is not available, it will be assumed that it was performed prior and will be considered as baseline. If assessment time is collected, the observed time as well as time of first dose will be used to determine pre-dose on study day 1 for baseline calculation. Unscheduled assessments will be used in the determination of baseline. However, if time is missing, an unscheduled assessment on Study Day 1 will be considered to have been obtained after study intervention.

Absolute and percent changes from baseline are defined as

absolute change = visit value – baseline value

percent change = $100 * (\text{visit value} - \text{baseline value}) / \text{baseline value}$

9.3 Study Day / Study Treatment Day

Day 1 is the day of start of study treatment, the day before is Day -1 (no Day 0 is defined). Study day / Study treatment day is defined relative to Day 1.

9.4 Definition of Duration and ‘time since’ Variables

Durations in days will be calculated by the difference of start and stop date + 1 (e.g. survival time (days) = date of death – date of first study intervention + 1) if not otherwise specified.

Date of first study intervention is defined as the date of the first administration of bintrafusp alfa during the study.

The time since an event (e.g. time since first diagnosis) will be calculated as reference date minus date of event. In general, the reference date will be the date of first study intervention.

The time to an event will be calculated by the difference between the time of event and the reference date + 1 if not otherwise specified. For example, survival time (days) = date of death - date of first study intervention + 1.

9.5 Conversion Factors

The following conversion factors will be used to convert days into months or years:

1 week = 7 days, 1 month = 30.4375 days, 1 year = 365.25 days.

9.6 Date of Last Contact

The date of last contact will be derived for participants not known to have died at the analysis cut-off using the latest complete date prior to or at the data cut-off date among the following:

- All participant assessment dates (blood draws (laboratory, PK), vital signs, performance status, electrocardiogram (ECG), tumor assessments, quality of life assessments)
- Start and end dates of anti-cancer therapies administered after study treatment discontinuation.
- AE start and end dates
- Last known to be alive date collected on the 'Survival Follow-up' eCRF (do not use follow-up date)
- Study drug start and end dates (including reinitiation of treatment)
- Date of discontinuation on disposition eCRF pages (do not use if reason for discontinuation is lost to follow-up)

Only dates associated with actual examinations of the participant reported in the eCRF will be used in the derivation. Dates associated with a technical operation unrelated to participant status such as the date a blood sample was processed will not be used. Assessment dates after the cut-off date will not be applied to derive the last contact date.

Data collected after reinitiated treatment will be considered in the derivation of the last known to be alive date.

CCI

CCI

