 - Patients with SD or PR should continue treatment until disease progression, or any other discontinuation criterion is met.
- Safety Follow-up will continue until 12 weeks after the last dose of bintrafusp alfa. The 12-week Safety Follow-up is allowed to be conducted via telephone calls or patient chart reviews unless there is a medical necessity requiring a clinical visit.
- Long-term Follow-up should be performed every 12 weeks after the Safety Follow-up according to the Schedule of Activities (see Table 1). Long-term Follow-up should be performed by chart reviews or telephone calls.
- Survival Follow-up will continue until the end of study as defined in Section 4.4. After stipulated end of study, Survival Follow-up may continue until the last participant has died or at the discretion of the Sponsor.

The overall study design is shown in Figure 1. A detailed Schedule of Activities (SoA) is provided in Section 1.3.

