14.2.13 Overall Survival (Secondary Endpoint)

Overall survival (OS) is defined as the time from first administration of study treatment to the date of death due to any cause:

OS = (date of event or censoring – date of the first dose + 1)/30.4375 (months).

For participants alive at the time of data cut-off date or who are lost to follow up, OS will be censored at the last date known to be alive. The date of event / censoring is defined in Table 8.

Table 8 Survival Event / Censoring

Survival Status	Date of event/censoring	Censoring
Participants alive or lost to follow-up before or at cut-off date	Last date known to be alive	Yes
Participants who died before or at cut-off date	Date of death	No

Last date known to be alive will be derived as specified in Section 9.6.

The analysis of OS time will be performed with a Kaplan-Meier method with the same approach as for PFS described in section 14.2.4. Kaplan-Meier estimates (product-limit estimates) will be presented together with a summary of associated statistics including corresponding two-sided 95% CIs. OS rates with their CI at 3, 6, 9, 12, 18 and 24 months will be presented, as well as the number of participants at risk and failed. Censoring reasons will also be described. Censoring reasons are as follows:

- Alive at cut-off date
- Withdrawal of consent
- Lost to follow-up

OS will also be presented graphically with Kaplan-Meier figures.

A participant listing will provide the following information: participant identifier, age, sex, race, date of first study intervention, date of event/censoring, event/censoring reason, time to event.

CCI

CCI

15 Safety Analyses

Analysis set: SAF

The subsections in this section include specifications for summarizing safety endpoints that are common across clinical studies such as adverse events, laboratory tests and vital signs.

Additional analyses may be performed on safety events to explore specific risk factors.

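### SAP 9.6 discards contacts after the cut-off that show a participant alive, while Table 8 counts earlier deaths whenever they are learned; late OS is biased low to the extent that such deaths come to light before database lock

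*SAP*

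**What the plan says.** Four places in the SAP and one in the protocol fix the OS dates.

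- **SAP 9.6** derives the last-contact date "using the latest complete date prior to or at the data cut-off date among the following" a list of sources: assessments, adverse-event dates, later anticancer therapy, the survival follow-up form, dosing and disposition. It then states: "Assessment dates after the cut-off date will not be applied to derive the last contact date".
- **SAP 14.2.13** links OS to that date: "Last date known to be alive will be derived as specified in Section 9.6". On who is censored it says: "For participants alive at the time of data cut-off date or who are lost to follow up, OS will be censored at the last date" they are known to be alive.
- **SAP Table 8** makes an event of "Participants who died before or at cut-off date", at the date of death. It does not say by when the death must be known.
- **SAP 9.1** says that "data after cut-off may be incomplete and subject to further change and will not be used for summary statistics, statistical analyses, listings or imputations". Its only stated exception concerns stop dates and outcomes of adverse events.
- **Protocol 4.1** sets the contact rhythm off treatment: "Long-term Follow-up should be performed every 12 weeks after the Safety Follow-up". Protocol Table 1 allows 2 weeks either side.

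SAP 6.1 keeps OS, its Kaplan-Meier curves, a subgroup forest plot and OS follow-up time in the single analysis at the 15 February 2022 cut-off. The OS rates at 3 to 24 months are specified in SAP 14.2.13.

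**The concern.** Kaplan-Meier estimation assumes that censoring does not depend on outcome. Here it can. A site that calls a participant after the cut-off may learn of a death dated before the cut-off, which then counts as an event. If the same call finds her alive, it is ignored and she stays censored at her previous contact. In the last weeks before the cut-off, deaths then enter the numerator while survivors of those weeks are missing from the risk set. The estimated late hazard is too high and the tail of the curve too low.

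The trial has one arm, so no control arm carries the same error, and OS rates will be read against outside figures. Most follow-up time is probably off treatment, where contacts are sparse: protocol 2.2 reports a median treatment duration of 9.6 weeks in the Phase I cohort.

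**Working it through.** **1. The rules side by side**

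| Learned after the cut-off | Effect on OS under the SAP |
|---|---|
| Death dated on or before the cut-off | Event at date of death (Table 8, no limit on when it is learned) |
| Contact or assessment showing the participant alive | Not used; censored at the last contact on or before the cut-off (9.6) |
| Death dated after the cut-off | Not an event, and does not move the censoring date |

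Example: a participant is reached alive on 7 December 2021 and again 84 days later, on 1 March 2022. She was alive on 15 February 2022 but is censored on 7 December, which is 24 + 31 + 15 = 70 days, or 10 weeks, early.

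**2. The plan's own figure.** SAP 14.2.4 classes a participant as lost to follow-up when the last alive date is more than 14 weeks before the cut-off. The interval plus the window gives 12 + 2 = 14 weeks, so the figure is reproduced. (Three months under SAP 9.5 would be 3 × 30.4375 / 7 = 13.0 weeks.)

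**3. Average lag.** With contacts 12 weeks apart and a cut-off falling at random between them, the expected lag is 12 / 2 = 6 weeks. Simulation gives 6.0 weeks, with a 95th percentile of 11.6 to 11.9 weeks.

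**4. Size when deaths in the final gap are known**

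Inputs from the documents:
- 135 participants (protocol 1.1).
- Cut-off 12 months after the last global participant (protocol 9.4.4).
- Contacts every 2 weeks on treatment, at 28 days and 12 weeks after the last dose, then every 12 weeks ± 2 (protocol Table 1).
- Median treatment about 2.2 months, from the Phase I 9.6 weeks.
- Median OS 8.3 and 11 months (protocol 2.2).

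Assumptions: median OS of 13 months as an upper case, exponential OS, uniform accrual over 9 or 12 months, and the share of final-gap deaths that is known. Each scenario used 1,500 simulated trials. The true rate is S(18) = 0.5^(18/median); for a median of 11 months, 0.5^(18/11) = 32.2%. The comparator counts all deaths and censors survivors at the cut-off.

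18-month OS, all final-gap deaths known:

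| Median OS (months) | Accrual (months) | True | SAP rule | Survivors censored at cut-off | Difference |
|---|---|---|---|---|---|
| 8.3 | 9 | 22.2% | 18.9% | 22.4% | −3.5 |
| 8.3 | 12 | 22.2% | 20.2% | 22.3% | −2.1 |
| 11 | 9 | 32.2% | 27.9% | 32.0% | −4.1 |
| 11 | 12 | 32.2% | 29.8% | 32.1% | −2.3 |
| 13 | 9 | 38.3% | 34.2% | 38.4% | −4.2 |
| 13 | 12 | 38.3% | 36.0% | 38.4% | −2.4 |

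- Other times: 0 at 6 months, −0.3 to −0.4 at 12 months, −1.2 to −1.9 at 15 months. The median moves by 0 to 0.3 months.
- With half of the final-gap deaths known, the 18-month shortfall of the SAP rule is 1.1 to 2.2 points.
- With none known, it is about 0.

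**5. Size when deaths and survival are both learned at the next scheduled contact.** This is closer to practice. For median OS 11 months and 12-month accrual:
- Lock 6 weeks after the cut-off: 30.5% under the rule against 32.3%.
- Lock 14 weeks after: 29.7% against 32.0%.

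With 18-month accrual the shortfall was 0.7 to 1.4 points across medians of 8.3 to 13 months. A separate run over accrual of 12 or 18 months gave 0.9 to 2.3 points, with the corrected rule within about 0.5 points of the truth. With nothing learned after the cut-off, the two rules agree and neither is biased.

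**6. The 24-month rate.** With 12-month accrual, maximum follow-up is 12 + 12 = 24 months, so nobody is at risk at 24 months under either rule. Any difference there is only the last Kaplan-Meier step carried forward.

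**The case against.** The strongest reply is that the SAP can be read symmetrically. SAP 9.6 applies to participants not known to be dead at the cut-off, which could mean dead as known on that day, and SAP 9.1 bars later data. Deaths and survival learned late would then both be ignored, and the bias disappears. This reading is possible. But SAP 9.1 concerns data after the cut-off, and a death dated before it is not plainly such data; Table 8 classifies by date of death alone. No visible text excludes a death because it was reported late. What stands is that the bias is conditional.

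Other points on that side:

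- **Size.** With median OS 10 months and 12-month accrual, the 18-month shift is about 2 points, against a standard error of about 4.4 points with about 14 participants at risk. This is fair, though the shift is systematic.
- **Harm from a one-sided fix.** In the same setting the true 18-month rate is 28.7%. If all survivors are moved to the cut-off but only half of the final-gap deaths are known, the estimate is 29.8%; with none known it is 31.0%. This stands, and the fix must treat both sides alike.
- **Lag.** SAP 9.6 also uses adverse-event and subsequent-therapy dates, so 6 weeks from scheduled contacts is an upper estimate. On treatment the loss is at most about 2 weeks.
- **Protocol.** Protocol Table 12 censors OS at last contact. It does not itself restrict contacts to those before the cut-off, so the correction does not conflict with it.

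A reader might infer more than the documents support: that deaths are certainly complete to the cut-off, that the 24-month rate is understated by several points, or that OS follow-up time is understated. The documents do not say when deaths are learned. The 24-month comparison has nobody at risk under 12-month accrual. The derivation of follow-up time is not visible, so its effect cannot be checked.

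**Conclusion.** The point holds in conditional form. As written, the OS rule uses late information about deaths and discards late information about survival. The bias is downward, confined to the tail of the curve, and grows with the share of pre-cut-off deaths learned between the cut-off and lock.

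A reasonable working size is 1 to 2 points at 18 months, rising to about 4 in the most unfavourable case examined. These figures rest on exponential OS and on assumed accrual length, lock delay and death ascertainment, none of which the documents give. Conclusions based on the median or on rates up to 12 months would not change. OS is a secondary endpoint without a planned test, and the primary ORR analysis is untouched. The change is worth making because the error is systematic and cheap to remove.

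**What to change.** In SAP 9.6 and Table 8, state:

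> A participant shown by any contact, assessment or death dated after the cut-off to have been alive at the cut-off is censored for OS at the cut-off date. Every other participant without a death on or before the cut-off is censored at the last contact on or before it.

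Two additions are needed:

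- List this in SAP 9.1 as an explicit exception to the rule on data after the cut-off; otherwise the SAP contradicts itself.
- State that survival information received up to database lock is used in the same way for deaths and for survivors. This also settles whether late-reported deaths count.

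The cost is a few sentences and a small change to one derivation. Survival status after the cut-off must also be cleaned, and collected with equal effort for deaths and survivors, because tracing only survivors would bias OS upward.

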9.8 Definition of On-treatment Period

The on-treatment period is defined as the time from the first study intervention administration to the last study intervention administration date + 30 days or the earliest date of subsequent anticancer drug therapy minus 1 day, whichever occurs first, unless otherwise stated.

For participants with treatment ongoing at cut-off date, all data from the first study intervention up to the cut-off date will be considered under the on-treatment period.

Any systemic anticancer therapy, any anticancer surgery and any anticancer radiotherapy as documented in the “Anti-cancer treatment after discontinuation details”, “Radiotherapy after discontinuation details” and “Surgery after discontinuation details” eCRF pages will be considered as subsequent anticancer therapy.

The on-treatment period will include the initial treatment period as well as the reinitiation of treatment period, as applicable. Whether the participant reinitiates treatment (following the rules as outlined in the protocol) or not, the on-treatment period is defined as the time from the first study intervention administration to the last study intervention administration date + 30 days or the earliest date of subsequent anticancer drug (anticancer therapy, anticancer surgery and anticancer radiotherapy) therapy minus 1 day, whichever occurs first, unless otherwise stated.

For immune-related AEs as listed in Section 15.2.3.2, an expanded on-treatment period will be used as a default for any analysis: time from the first trial drug administration to the last trial drug administration date + 90 days, death OR to the earliest date of subsequent anticancer therapy minus 1 day, whichever occurs first, unless otherwise stated.

9.9 Imputation of Missing Data

Unless otherwise specified, all data will be evaluated as observed, and no imputation method for missing values will be used.

In all participant data listings, imputed values will be presented, and imputed information will be flagged.

Partial dates, which are not to be imputed according to the IAP, will be presented in the format like “____YYYY”. If values are imputed according to the IAP, imputed values will be presented in participant data listings and imputed information will be flagged.

Missing statistics, e.g. when they cannot be calculated, should be presented as “nd” for “not determined”. For example, if $n = 1$, the measure of variability (StD) cannot be computed and should be presented as “nd”.

Age calculation	Incomplete dates (date of informed consent, date of birth) for the calculation of age will be imputed as follows: 
• In case of missing day for at least one date, but month and year available for both dates: the day of informed consent and the day of birth will be set to 1.• In case of missing month for at least one date, but year available for both dates, the day and the month of informed consent and the day and month of birth will be set to 1.• In all other cases, the incomplete dates will not be imputed.
Disease history	Incomplete dates for disease history (e.g. initial diagnosis date, date of documented, locally advanced, inoperable or metastatic disease diagnosis, date of response or progression in prior treatment) will be imputed as follows: 
• If the day is missing, it will be imputed to the 1st day of the month.• If both day and month are missing, the month and day will be imputed as January 1st.• If the date is completely missing, no imputation will be performed.
Adverse events	Incomplete AE-related dates will be imputed as follows:

	
 • In case the onset date is missing completely or missing partially but the onset month and year, or the onset year are equal to the start of study treatment then the onset date will be imputed by the minimum of start of study treatment and AE resolution date (if not missing). • In all other cases, the missing onset day or missing onset month will be imputed by 1. • Incomplete stop dates will be imputed by the last day of the month (if day is missing only), if not resulting in a date later than the date of participant’s death. In the latter case, the date of death will be used to impute the incomplete stop date. • In all other cases the incomplete stop date will not be imputed.

Previous and concomitant medication
	
Incomplete dates for previous and concomitant medications will be imputed as follows:
 
For start date of medication:
 
 • If the day is missing, it will be imputed to the 1st day of the month. • If both day and month are missing, the month and day will be imputed as January 1st. • If the date is completely missing, no imputation will be performed. 
For end date medication:
 
 • If the day is missing, it will be imputed to the last day of the month. • If both day and month are missing, the month and day will be imputed as December 31st. • If the date is completely missing, no imputation will be performed. 
In case the imputation results in a date later than the date of participant's death, then the date of death will be used to impute the incomplete stop date.

For identification of previous or concomitant medications/procedures, rules presented in [Table 5](#) and [Table 6](#) below will be used to define if a medication/procedure is considered as a previous, concomitant or both previous and concomitant medication/procedure.

Table 5 Stopping rules for medication/procedure end dates

End date of medication/procedure			Stopping rule
Day	Month	Year	
UNK	UNK	UNK	After treatment start (ongoing)
UNK	UNK	< Treatment start (year)	Before treatment start

End date of medication/procedure			Stopping rule
Day	Month	Year	
UNK	UNK	>= Treatment start (year)	After treatment start
UNK	< Treatment start (month and year)		Before treatment start
UNK	>= Treatment start (month and year)		After treatment start
< Treatment start (complete date)			Before treatment start
>= Treatment start (complete date)			After treatment start

UNK = Unknown.

Table 6 Rules to define previous and/or concomitant medication

Start date of medication/procedure			Stopping rule (see Table 5)	Medication/procedure
Day	Month	Year		
UNK	UNK	UNK	Before treatment start	Previous
UNK	UNK	UNK	After treatment start	Previous and concomitant
UNK	UNK	<= Treatment start (year)	Before treatment start	Previous
UNK	UNK	<= Treatment start (year)	After treatment start	Previous and concomitant
UNK	UNK	> Treatment start (year) and <= Treatment end + 30 days (year) OR the earliest date of subsequent anticancer drug therapies minus 1 day, whichever occurs first.	After treatment start	Concomitant
UNK	<= Treatment start (month and year)		Before treatment start	Previous
UNK	<= Treatment start (month and year)		After treatment start	Previous and concomitant
UNK	> Treatment start (month and year) and <= Treatment end + 30 days (month and year) OR the earliest date of subsequent anticancer drug therapies minus 1 day, whichever occurs first.		After treatment start	Concomitant
<= Treatment start (date)			Before treatment start	Previous
<= Treatment start (date)			After treatment start	Previous and concomitant

Start date of medication/procedure			Stopping rule (see Table 5)	Medication/procedure
Day	Month	Year		
> Treatment start (date) and <= Treatment end + 30 days (date) OR the earliest date of subsequent anticancer drug therapies minus 1 day, whichever occurs first.			After treatment start	Concomitant

UNK = Unknown.

Dates of study treatment	
Start date of study treatments:
 
 No imputation will be done. 
End date of study treatments:
 
In case the last date of study drug is missing or incomplete the date of last administration of study drug will be taken from the treatment termination eCRF pages.
 
 If the last date of study drug is completely missing and there is no End of Treatment eCRF page and no death date the participant should be considered to be ongoing and use the cut-off date for the analysis as the last dosing date If the last date of study drug is completely or partially missing and there is EITHER an End of Treatment eCRF page OR a death date available (within the cut-off date) then imputed last dose date is: 
 = 31DECYYYY, if only Year is available and Year < Year of min (EOT date, death date) = Last day of the month, if both Year and Month are available and Year = Year of min (EOT date, death date) and Month < the month of min (EOT date, death date) = min (EOT date, death date), for all other case
Death date	
For the purpose of survival analyses (PFS and OS) partially missing death dates will be imputed as follows:
 
If only the day is missing, the death date will be imputed to the maximum of the (non-imputed) day after the date of last contact and the 15th day of the month.
 
Otherwise it will not be imputed.
 
In listings, the imputed date of death will be presented with a flag indicating the level of imputation.

CCI

CCI

CCI

CCI

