 - a. Participants with diabetes Type 1, vitiligo, alopecia, psoriasis, hypo- or hyperthyroid disease not requiring immunosuppressive treatment are eligible.
 - b. Participants requiring hormone replacement with corticosteroids are eligible if the steroids are administered only for the purpose of hormonal replacement and at doses ≤ 10 mg of prednisone or equivalent per day.
 - c. Administration of steroids for other conditions through a route known to result in a minimal systemic exposure (topical, intranasal, intro-ocular, or inhalation) is acceptable.
7. Known severe hypersensitivity (Grade ≥ 3 National Cancer Institute-Common Terminology Criteria for Adverse Events v5.0 [NCI-CTCAE v5.0]) to investigational product (bintrafusp alfa) or any components in its formulation, any history of anaphylaxis, or recent, within 5 months, history of uncontrollable asthma.
8. Persisting Grade > 1 NCI-CTCAE v5.0 toxicity (except alopecia and vitiligo) related to prior therapy; however, sensory neuropathy Grade ≤ 2 is acceptable.
9. Clinically significant cardiovascular/cerebrovascular disease including: cerebral vascular accident/stroke (< 6 months prior to enrollment), myocardial infarction (< 6 months prior to enrollment), unstable angina, congestive heart failure (\geq New York Heart Association Classification Class II), or serious cardiac arrhythmia. Participants with history of bleeding diathesis or recent major bleeding events considered by the Investigator as high risk for investigational drug treatment are also excluded.
10. Severe and/or clinically relevant acute or chronic diseases which, in the opinion of the Investigator, might impair the participant's tolerance for the study or ability to consistently participate in study procedures.

Prior/Concomitant Therapy

11. Has received prior cancer treatment with any other immunotherapy or checkpoint inhibitors, such as anti-PD-1, anti-PD-L1, anti-PD-L2, anti-CTLA-4, or any other immune-modulating mAb (e.g. any other antibody or drug specifically targeting T-cell co-stimulation, checkpoint pathways or immune-suppressive pathways [e.g. TGF- β]).
12. Concurrent treatment with prohibited drugs (see Section 6.5.2).
13. Systemic therapy with immunosuppressive agents within 7 days before the start of study intervention; or use of any investigational drug within 28 days before the start of study intervention.

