12.1 Previous and concomitant medications

Concomitant treatments are medications, other than study treatment, which are taken by participants any time during the on-treatment period, see Section 9.8. All medications starting the same day as study drug will be considered as concomitant. Medications starting 30 days after the last dose of study treatment will also be considered as concomitant.

Previous medications are medications, other than study treatment and pre-medications for study treatments, which started before first administration of study treatments.

A medication may be classified as both concomitant and previous. The respective flags will be derived based on start and end date.

Concomitant and previous treatment each will be summarized by number and percentage of participants from the “Concomitant Medication Details” eCRF. ATC-2nd level and PT will be tabulated as given from the WHO-DD dictionary most current version at the time of the database lock. If any previous or concomitant medication is classified into multiple ATC classes, the medication will be summarized separately under each of these ATC classes. The summary tables will be sorted by decreasing frequency of drug class and decreasing frequency of drug name in a given drug class. In case of equal frequency regarding drug class (respectively drug name), alphabetical order will be used. In case any specific medication does not have an ATC classification level 2 coded term, it will be summarized under “Unavailable ATC classification” category. Each participant will only be counted once, even if he/she received the same medication at different times.

Specific rules will be used to define if a medication/procedure is considered as a previous, concomitant or both previous and concomitant medication/procedure as detailed in Section 9.9.

Previous and concomitant medications will be presented in listing and include: participant identifier, age, sex, race, PT, medication name as provided by the Investigator, start date, end date, dose, dose units, frequency, route, reason for the medication.

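### SAP Table 6 flags every non-premedication drug with a complete Day 1 start date as previous, so drugs first given after the first infusion are miscounted against the SAP 12.1 definition

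*SAP*

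**What the plan says.** SAP 12.1 gives the definitions. A previous medication is one, other than study treatment and its premedication, "which started before first administration of study treatments". For same-day starts it adds: "All medications starting the same day as study drug will be considered as concomitant". It allows a drug to carry both flags, bases the flags on start and end date, and refers to Section 9.9 for the detailed rules.

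Section 9.9 supplies those rules in two steps.

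- Table 5 reads the end date. A complete end date meeting ">= Treatment start (complete date" counts as stopping after treatment start. A wholly unknown end date is read as "After treatment start (ongoing".
- Table 6 combines that result with the start date. For complete dates, a start meeting "<= Treatment start (date" gives *Previous* if the drug stopped before treatment start and "Previous and concomitant" if it stopped after. *Concomitant* alone requires "> Treatment start (date) and <= Treatment end + 30 days (date" or, if earlier, a start no later than the day before subsequent anticancer drug therapy.

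SAP 9.3 defines Day 1 as the day study treatment starts. SAP 12.2 summarizes premedication separately from its own eCRF page. SAP 6.1, which cuts the analyses down to an abbreviated CSR, keeps the previous and concomitant medication outputs.

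**The concern.** The definition and the derivation draw the boundary in different places. In 12.1 the boundary is the first administration. In Table 6 it is the end of the calendar day of the first administration. A drug first given after the Day 1 infusion is not previous under 12.1 but is previous under Table 6, and Table 6 is what will be programmed.

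Such drugs are foreseeable. Premedication is optional for the first two infusions (Protocol 6.9.1), infusion reactions can begin during or after the infusion on the same day (SAP 15.2.3.1), and the protocol provides for drug treatment of them. Only premedication is carved out of the previous-medication definition; reaction treatment is not.

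What is at stake is the accuracy of a descriptive table of what participants were taking before study drug. Any such entry overstates previous use of that drug class.

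**Working it through.** The plan states no figure on this point, so there is none to reproduce. The check applies the complete-date rules of Tables 5 and 6 to a grid of start and end days, first as written and then with a strict boundary.

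**Step 1: which Table 5 result can a Day 1 start have?** A drug started on Day 1 cannot end before Day 1. Its end date is on or after treatment start, or unknown. Table 5 returns *after treatment start* in every case.

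**Step 2: which Table 6 row follows?** The condition 'start on or before treatment start' is met by equality, and the stopping rule is 'after'. The result is always both flags. The *Concomitant*-only row requires a start strictly after treatment start, so Day 1 can never reach it.

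**Step 3: the grid.** Start days −5, −1, 1 and 2 were crossed with end days −1, 1, 2, 10 and unknown, leaving out ends before starts (17 cases).

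| Start day | End day | As written | Strict boundary |
|---|---|---|---|
| −5 or −1 | −1 | Previous | Previous |
| −5 or −1 | 1, 2, 10 or unknown | Both flags | Both flags |
| 1 | 1, 2, 10 or unknown | Both flags | Concomitant |
| 2 | 2, 10 or unknown | Concomitant | Concomitant |

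Only the four Day 1 cases change; the other 13 do not. The equality sign is the sole cause.

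**Step 4: which Day 1 flags are wrong under 12.1?**

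- Premedication: outside the definition, so not affected.
- Another drug taken on Day 1 before the infusion: started before first administration, so the previous flag is right.
- A drug first given on Day 1 after the infusion: not started before first administration, so the previous flag is wrong.

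**Step 5: size.** The documents do not say how many participants start a non-premedication drug after the Day 1 infusion. For treatment of infusion reactions, Protocol 2.3 reports drug-related reactions in fewer than 5% of participants at study initiation, all Grade 1 or 2. With the planned 135 participants:

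0.05 × 135 = 6.75, so fewer than 7 participants.

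This is an expected ceiling if the earlier rate carries over. It covers reactions to any infusion and does not require drug treatment, so the first-infusion share given a drug would be smaller. It does not bound Day 1 starts for other reasons.

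**The case against.** The strongest defence is that both flags are an inclusive convention for a date that cannot be resolved. Section 12.1 derives the flags from dates, and the fields it names for the medication listing include no clock time. With dates alone, drugs given before and after the Day 1 infusion cannot be told apart, and a strict boundary drops genuine pre-infusion starts from the previous table. This stands as a limit on any fix. It does not reconcile the two sections, because 12.1 states no such convention. Nor is it a missing-date rule, since the rows at issue are those for complete dates.

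Three stronger readings are tempting, and the documents do not support them.

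- *Table 6 breaches the same-day sentence of 12.1.* It does not. That sentence makes Day 1 starts concomitant, and Table 6 flags them so. Section 12.1 does not say 'only' and allows both flags. The conflict is with the definition of previous alone.
- *Every Day 1 start is misclassified, so a large share of the 135 participants is affected.* Drugs taken before the infusion are correctly previous, and the documents give no rate from which to derive such a share.
- *The table could mislead a check on eligibility*, for example the exclusion of "Systemic therapy with immunosuppressive agents within 7 days before the start of study intervention" (Protocol 5.2). No section uses this table for that purpose. Eligibility is confirmed at Screening, and important deviations have their own table and listing (SAP 10.2.1). The medication listing shows the start date and the reason for use, so a drug given on Day 1 for a reaction can be identified there.

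**Conclusion.** The inconsistency is real and minor. Under the complete-date rows of Table 6, all non-premedication drugs started on Day 1 enter the previous-medication table, including those first given after the infusion, which 12.1 excludes. The error can only inflate previous-medication counts. How many participants it touches is unknown and probably few. The one figure that can be derived, fewer than 7 of 135 for infusion reactions, assumes that the below-5% rate in Protocol 2.3 applies here. Concomitant-medication counts, efficacy, adverse event analyses and eligibility decisions do not change. It is worth correcting because the output is kept for the abbreviated CSR and the remedy is short.

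**What to change.** In the complete-date rows of Table 6 only:

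- change `<=` to `<` in the *Previous* row and in the row that gives both flags;
- change `>` to `>=` at the start of the *Concomitant* row.

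Make the three edits together. With only the `<` edits, a Day 1 start would fall in no category. The edit to the *Previous* row changes no flag, since a Day 1 start cannot stop before Day 1, but it keeps one boundary throughout.

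Leave the partial-date rows alone. They use the same boundary at month and year level, where an inclusive rule may be deliberate caution about incomplete dates.

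Add one sentence to 12.1 saying that flags use dates only and that a non-premedication drug started on Day 1 is counted as concomitant only. There is a precedent in SAP 9.2, which takes an unscheduled Day 1 assessment without a time as made after study intervention.

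The cost is a few characters in three rows, one sentence and the matching line of code. The downside is that a non-premedication drug taken on Day 1 before the infusion loses its previous flag. If the sponsor prefers to keep the inclusive boundary, the alternative is to amend the 12.1 definition and footnote the table. Either way the two sections should agree.
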